A prospective, randomized clinical trial to compare vestibular incision supraperiosteal tunnel access (VISTA) and sulcular tunnel access root coverage procedures with coronally advanced flap and acellular dermal matrix (ADM) to treat teeth with gingival recession and lack of adequate keratinized tissue. A pilot study.

Study Protocol & Statistical Analysis Plan

NCT03566108

August 31, 2022

[name], MS, Principal Investigator

University of Alabama at Birmingham
Birmingham, AL 35294

A prospective, randomized clinical trial to compare vestibular incision suprapariosteal tunnel access (VISTA) and sulcular tunnel access root coverage procedures with coronally advanced flap and acellular dermal matrix (ADM) to treat teeth with gingival recession and lack of adequate keratinized tissue. A pilot study.

1. Study Protocol 1. Objectives/Specific Aims:

This investigator-initiated study will compare two commonly used soft tissue grafting techniques [vestibular incision suprapariosteal tunnel access (VISTA) vs. sulcular tunnel access root coverage procedures with the uses of acellular dermal matrix (ADM)] to achieve coronal flap advancement and root coverage as well as augmentation of soft tissue at intraoral tooth sites. Research data and daily clinical observations reveal that teeth with gingival recession and a lack of adequate keratinized tissue (KT) are more prone to persistent gingival inflammation, dentinal sensitivity, radicular (root) caries (tooth decay), faster periodontal attachment loss, and compromised plaque control. Soft tissue grafting (by various techniques) aims at changing the quality, quantity and placement of the soft tissue around teeth by covering exposed root surfaces and creating or increasing the zone of keratinized mucosa (KM) surrounding the affected teeth. Both techniques tested have shown good clinical outcomes with regard to root coverage, but clinical reports of the VISTA technique and other similar techniques suggest that patients experience a decrease in site morbidity and discomfort post-operatively. To our knowledge, these 2 types of grafting techniques have not been compared in a prospective trial for differences in clinical (percentage of root coverage, amount of KT increase, tissue thickness increase, and practitioner-assessed esthetics) and patient-centered outcomes (pain, swelling, change in daily activities, and patient-assessed esthetics) in a controlled study.

2. Materials and Method:

Study population:

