A total of 40 patients seeking treatment at the UAB SOD Graduate Periodontology clinics will be recruited to participate in this study. The potential candidates will be approached during the treatment planning and/or pre-surgical visit in the periodontal clinic. The investigator/research staff will give the IRB approved consent form to the potential participants, explain the study, and obtain the patient demographics if the patient participate in the study.

Procedures:

Normal dental appointment: Patients that are seen at the school of dentistry for regular dental care and evaluation may be identified as plausible participants for the study based on the inclusion criteria, they will be scheduled for a screening appointment to determine eligibility for inclusion within the study. Screening/baseline visit: patient's electronic records will be reviewed to assess radiographic documentation. If the x-ray is at least one year old a new radiograph will be obtained. Two trained and calibrated examiners will conduct clinical and radiographic evaluations to determine eligibility according to the above criteria. Study visits and objectives will be explained to all participants. IRB approved written informed consent will be obtained from all the participants. Photos will be obtained at the screening visit and at each subsequent visit (1-7) to evaluate healing of the tissue.

Clinical parameters that will be captured include:

- Probing depth (PD) measurements
- Bleeding on probing (BOP)
- Plaque Index (PI, Silness & Loe): A modification of the Silness and Loe Plaque Index will be used full mouth. Categories 2 and 3 from the original index will be collapsed into a single

category so that examiners only have to distinguish between visible plaque and plaque that cannot be seen but is detectable with the probe. A single score will be recorded for each tooth. A single score 0 to 2 will be recorded for buccal and lingual/palatal surface of each tooth examined as follows:

0 = No plaque

1 = A film of plaque adhering to the free gingival margin and adjacent area of the tooth which cannot be seen with the naked eye. But only by using disclosing solution or by using probe.

2 = Moderate accumulation of deposits within the gingival pocket, on the gingival margin and/or adjacent tooth surface, which can be seen with the naked eye.

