- Gingival Index (*GI*, Loe and Silness) at surgical site(s). A periodontal probe will be swept around the tooth sulcus at a depth of 1-2 mm. The examiner will determine the status of tissue health. A single score will be recorded for buccal and lingual/palatal surface of each tooth examined as follows:

0 = healthy tissue

1 = mild inflammation but no bleeding

2 = moderate inflammation with bleeding

3 = severe inflammation with a tendency toward spontaneous bleeding

- Width of keratinized tissue (KT) will be measured at tooth site(s) at the mid-buccal aspect from the mucosal margin to the mucogingival junction.
- Width of attached tissue (AT) will be calculated by subtracting PD from KM
- Tissue Thickness (TT1 and TT2) at the buccal mucosa will be measured during the surgical visit by horizontal transmucosal probing (sounding the bone) using an endodontic reamer after local infiltration of anesthetic prior to surgical site preparation. TT1 and TT2 will be measured at 2 mm and 5 mm from the mucosal margin, respectively.

Clinical photographs of the tooth site (s) will be obtained with one digital SLR camera.

Randomization: two groups (Participants will be randomized like the flip of a coin to one of the two groups listed.) Randomly generated treatment groups will be printed on note cards and placed in sealed opaque envelopes. Once the patient consents to participate in the study an envelope is opened, and the patient is then offered the allocated treatment regimen.

Group 1: will receive vestibular incision supraperiosteal tunnel access (VISTA) + Acellular Dermal Matrix (ADM) graft around teeth with gingival recession and lack of KT.

Group 2: will receive sulcular tunnel access + Acellular Dermal Matrix (ADM) graft around teeth with gingival recession and lack of KT.

Surgical visit (Visit 1): Patients will be anesthetized via infiltration around recipient tooth/teeth site(s). Study surgeon will confirm measurements taken at baseline with relation to width of keratinized tissue (KT) and evaluate thickness of mucosa (TT1 and TT2) as described above. Surgeon will then measure the recipient site to determine the size of graft needed and ensure that surgical treatment will avoid any vital structures. Soft tissue grafting procedures will include local anesthesia, monitoring of vital signs (bp, HR, O2 sat). Study surgeons will follow standard-of-care procedures for soft tissue as follows:

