The width of keratinized tissue (KT) will be assessed at visits 4, 5, 6 and 7. Tissue thickness (TT1 and TT2) will be evaluated at visits 5, 6 and 7. Clinical measurements will be collected by calibrated examiners. Measurements from all visits will be compared to baseline in order to evaluate the progression of healing over time up to 12 months post-op.
5. Patient satisfaction survey
This survey will be performed at visits 2 and 4 using a visual analogue scale (VAS) based questionnaire regarding esthetic appearance, pain, swelling, bruising, effects on daily activities. Esthetic evaluation by the patient will also be assessed at visits 6 and 7.
6. Pink Esthetics Score (PES)
This standardized assessment of esthetics will be performed at visits 6 and 7 by blinded, calibrated examiners.
7. Study participation and satisfaction survey to be completed at final study visit (visit 7)

Inclusion/Exclusion Criteria:

Inclusion Criteria	Exclusion Criteria
English speaking	Non-English speaking
At least 18 years old	Less than 18 years old
Must be a patient of the UAB Dental School	Smokers/tobacco users (>10 cigarettes/day)
Able to read and understand informed consent document.	Patients with systemic pathologies or conditions contraindicating oral surgical procedures or adversely affecting wound healing.
One or more adjacent teeth (up to four) with Miller class I or II gingival recession defects and ≤ 2mm of KT at each site to be treated.	Presence of active periodontal disease or radiographic interproximal bone loss or tooth malposition, which would yield a Miller class III or IV categorization for the recession defect.
Presence of periodontally healthy, non-carious neighboring teeth, healthy implants, or edentulous ridges on either side of the involved site(s)	Presence of frenulae or other soft tissue anomalies at the site(s) to be treated that, in the opinion of the investigators, will interfere with successful access and treatment of the soft tissue defects.
No anticipated need for restorative care at the teeth to be treated during the study period.	Previous soft tissue grafting at the site(s) to be treated

--	--

Group Table:

Group	Treatment	Number of participants
Group 1	Vestibular incision suprapariosteal tunnel access (VISTA) + Acellular Dermal Matrix (ADM) graft	20
Group 2	Sulcular tunnel access + Acellular Dermal Matrix (ADM) graft	20

3. Study Background:

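### The allocation envelope is opened at consent, before the operating surgeon reads baseline tissue thickness; opening it after that reading would cost little

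*Combined protocol and SAP*

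**What the plan says.** The order of events has to be assembled from several places in Section 2 (Materials and Method).

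- **Consent**, under the screening/baseline visit: "IRB approved written informed consent will be obtained from all the participants".
- **Allocation**, in the randomization paragraph: an envelope is opened as soon as consent is given, and "the patient is then offered the allocated treatment regimen".
- **Baseline thickness**, in the list of clinical parameters: TT1 and TT2 "will be measured during the surgical visit by horizontal transmucosal probing (sounding the bone) using an endodontic reamer after local infiltration of anesthetic", before the site is prepared.
- **Who reads it**, under Surgical visit (Visit 1): "Study surgeon will confirm measurements taken at baseline with relation to width of keratinized tissue (KT) and evaluate thickness of mucosa (TT1 and TT2".
- **Follow-up**: TT1 and TT2 are read again at visits 5, 6 and 7, and measurements from all visits are compared with baseline. Examiners are described as calibrated.
- **Patient scores**: VAS surveys at visits 2 and 4. "Esthetic evaluation by the patient will also be assessed at visits 6 and 7".

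Section 4 lists change in tissue thickness at 6 and 12 months as an outcome. The only blinding stated anywhere is for the Pink Esthetics Score examiners at visits 6 and 7.

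**The concern.** A thickness reading with an endodontic reamer depends on the operator's hand and eye. If the operator already knows which technique will follow, the reading can drift by arm without anyone intending it. Because the outcome is a change from baseline, such a drift passes into the treatment comparison, and blinding later examiners would not remove it.

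There is a second consequence. A patient who is offered a particular arm some time before surgery has an opportunity to decline it. The documents define neither an analysis population nor how such refusals would be handled, so losses of this kind could differ between arms.

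Both exposures come from the moment at which the envelope is opened, and nothing in the documents requires it to be opened that early.

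**Working it through.** **1. The plan's own figure.** Section 4 states 92% power with 20 and 20 patients, margin -1.0, true difference 0.1, SD 1.0 and one-sided alpha 0.025.
- Distance to the margin: 0.1 - (-1.0) = 1.1.
- Standard error: 1.0 × sqrt(2/20) = 0.316.
- Noncentrality: 1.1 / 0.316 = 3.48.
- Exact t power on 38 degrees of freedom: 92.4%. The normal approximation gives 93.6%.

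The stated power reproduces, and this point does not dispute it.

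**2. The sequence.**

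| Step | When | Arm can be known? |
|---|---|---|
| Consent | Screening/baseline visit | No |
| Envelope opened, regimen offered | Once the patient consents | From here on |
| Anesthesia, KT confirmation, TT1/TT2 | Visit 1 | Yes |
| Graft sizing, then arm-specific site preparation | Visit 1 | Yes, and now necessary |
| Patient VAS surveys | Visits 2 and 4 | Yes |
| TT1/TT2 again | Visits 5, 6, 7 | Yes; blinding not stated |

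The TT1/TT2 reading already comes before the first step that differs by arm. Opening the envelope between the two changes nothing in the order of surgery.

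**3. How a baseline shift carries through.** Change = follow-up - baseline. If baseline in one arm is read high by d on average, mean change in that arm falls by d, and so does the difference between arms. The documents name no analysis model. Adjusting for baseline with slope b would carry b × d instead of d.

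**4. Scale.** The documents give no value for d, so these are illustrations. They assume 20 analyzed per arm and express the shift in the arm difference in SDs of the outcome.
- 95% CI half-width for an arm difference: t(0.975, 38) × sqrt(2/20) = 2.024 × 0.316 = 0.64 SD.
- Shift of 0.2 SD: 0.2 / 0.64 = 31% of the half-width.
- Shift of 0.3 SD: 0.3 / 0.64 = 47%.
- With no true difference, the false-positive rate of a two-sided 5% t-test, from the noncentral t with noncentrality shift / 0.316, rises from 5% to 9.5% at 0.2 SD and 15.2% at 0.3 SD.

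**The case against.** The strongest reply is that this is an ordinary surgical trial. The surgeon cannot be blinded to the operation, the envelopes are opaque and sealed, and for patient-centered outcomes Section 4 itself calls the study a pilot. Much of this stands. Concealment before consent is protected and is not criticized here. But a surgeon who must know the arm in order to operate need not know it while taking the preceding measurement.

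A reader might infer more than the documents support:

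- **That patients are told the technique by name.** This is the natural reading of "the patient is then offered the allocated treatment regimen", but the text does not say so, and the consent form is not in the public copy.
- **That the patient surveys are biased because they follow allocation.** Outcomes always follow allocation. What can be said is that no patient masking is planned. Section 1 notes clinical reports on VISTA that "suggest that patients experience a decrease in site morbidity and discomfort post-operatively", but Section 3 calls the decrease purported and Section 6 names no direction. Nothing shows that patients are told to expect less pain with VISTA.
- **That patient blinding would be easy.** One arm has a vestibular incision that is sutured; the other has sulcular incisions. Patients may see the site before the first survey at visit 2, so silence would give partial masking at best.
- **That baseline KT is equally exposed.** At visit 1 the surgeon only confirms a KT reading taken at baseline. TT1 and TT2 have no earlier reading described.

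Readiness is also a fair objection: the documents do not say whether preparation before the day differs by technique.

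**Conclusion.** The point holds for baseline thickness. On the document's own sequence, the first TT1/TT2 reading is made by the operating surgeon after the arm can be known, with no masking stated, and it is the baseline for a listed outcome. The opportunity to decline after allocation also follows from the text, although the documents give no figure for how often it would happen.

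For patient-scored outcomes the conclusion is limited to this: they are not masked as planned, could be masked only in part, and should not be presented as blinded.

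The size is unknown. The 0.2 to 0.3 SD range is an assumption, and the result that it would be 31% to 47% of the 0.64 SD half-width indicates scale only. The verdict also assumes that thickness change is computed from TT1/TT2. Section 2 supports this by comparing all visits with baseline, but Section 4 describes thickness change by intrasulcular probing and tissue transparency, and the two descriptions should be reconciled. This is an inexpensive improvement to the design; it does not invalidate the randomization or the stated power.

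**What to change.** Amend the randomization paragraph along these lines: *The envelope will be opened at visit 1, after local anesthesia and after the KT confirmation, TT1 and TT2 have been recorded, and before any arm-specific site preparation. The time of opening will be recorded.*

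As a secondary step, where consent allows, staff should not volunteer the technique to the patient before the visit 2 and visit 4 VAS surveys. The report should say that masking was partial, because the vestibular incision or sutures may be seen, and that patient-scored results are not reliably blinded.

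The cost is a change of wording in the protocol and, for the secondary step, in what patients are told. The practical downside is that the surgeon must be ready for either technique on the day. The change protects only the baseline reading; follow-up thickness readings remain unmasked unless the protocol says otherwise.

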Soft tissue grafting for root coverage and alteration of the quality of gingival tissue surrounding teeth was originally described in 1956 using a Lateral Pedicle Flap.¹ Since that time, myriad techniques and materials have been described to improve clinical outcomes and patient acceptance.²⁻⁶ Systematic reviews and meta-analyses have concluded that root coverage and KT gain at sites with Miller class I or II defects could be reliably achieved with the use of allogeneic donor tissue as well as autogenous connective tissue harvested from a patient’s palate.⁷⁻⁹ Use of a tunnel technique has also been shown to demonstrate decreased post-operative discomfort when compared with a standard coronally advanced flap.¹⁰ Recently, there has been renewed interest in vestibular incisions, originally described in 1912¹¹, for the coronal advancement of gingival tissues with the use of graft materials due to purported decrease in post-operative discomfort and healing time.

Given the increase in the number of procedures performed, this study seeks to compare two established tunneling technique procedures with the use of allogeneic soft tissue graft materials to evaluate clinical and patient-centered outcomes to determine if there are any notable differences in post-operative healing and clinical outcomes associated with each technique.

4. Outcomes Measures

Outcomes will be measures by an evaluation of the following:

- Percentage previously visible root surface that has been covered by gingiva at 6- and 12-months following grafting with VISTA and sulcular tunnel access with ADM as compared to the baseline data.
- KT width as measured in mm by practitioner at 6- and 12-month following grafting with VISTA and sulcular tunnel access with ADM
- Change in tissue thickness evaluated with gentle intrasulcular probing and level of transparency of the grafted sites at 6 and 12 months.
- Practitioner-assessed esthetic outcomes using a standardized pink esthetic scale (PES) at 6 and 12 months postoperatively.
- Patient-assessed esthetic outcomes of root coverage and soft tissue appearance at 6 and 12 months post-operatively
- Patient centered outcomes including pain, bleeding, swelling, change in daily activities at 1 week and 1 month postoperatively, see attached Visual Analog Scale (VAS)

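### Blinded assessment is stated only for the Pink Esthetics Score; the plan does not ensure that root coverage, KT and tissue thickness at 6 and 12 months are read without knowledge of the arm

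*Combined protocol and SAP*

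**What the plan says.** **Follow-up readers.** Section 2, Follow up visits, item 4 schedules KT at visits 4 to 7 and adds "Tissue thickness (TT1 and TT2) will be evaluated at visits 5, 6 and 7". On who takes the readings it says only "Clinical measurements will be collected by calibrated examiners", and it then has every visit compared with baseline. Root coverage is not listed in that item. Item 6 says of PES: "This standardized assessment of esthetics will be performed at visits 6 and 7 by blinded, calibrated examiners". No other examiner in the document is described as blinded.

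**Outcome list.** Section 4 describes the same assessments again:

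- Root coverage: "Percentage previously visible root surface that has been covered by gingiva at 6- and 12-months following grafting", with no assessor named.
- KT: "KT width as measured in mm by practitioner at 6- and 12-month following grafting".
- Thickness: "Change in tissue thickness evaluated with gentle intrasulcular probing and level of transparency of the grafted sites at 6 and 12 months", with no assessor named.
- PES: "Practitioner-assessed esthetic outcomes using a standardized pink esthetic scale (PES) at 6 and 12 months postoperatively".

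**Before surgery.** At screening, two trained and calibrated examiners carry out the evaluation. Under Randomization, the envelope is opened after consent. At Visit 1 the study surgeon confirms KT and takes the thickness readings. The method is given under Clinical parameters: "Tissue Thickness (TT1 and TT2) at the buccal mucosa will be measured during the surgical visit by horizontal transmucosal probing", using an endodontic reamer.

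**The concern.** The operator necessarily knows which access technique was used. For outcomes that someone else can read, a reader who does not know the arm is the available safeguard. Calibration is a different protection: it makes examiners agree with one another but does not hide the arm from them.

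Root coverage, KT and thickness are the main clinical outcomes. If the reader knows the arm, expectation can create a difference between the arms or hide one. Thickness is the most exposed, because its description in section 4 includes a visual judgement of transparency with no scale. Section 1 also reports a prior impression that VISTA is easier on patients. That impression is about comfort, not root coverage, but it shows that the two arms are not regarded as interchangeable.

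The plan already accepts the safeguard for PES at the same two visits, so its absence for the other three outcomes is hard to explain as a deliberate choice.

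**Working it through.** The plan states no figure for this point, so the check sets the sections side by side.

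**1. Who reads each outcome in section 4, and is blinding stated?**

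| Outcome | Reader in section 2, Follow up visits | Reader in section 4 | Blinding stated |
|---|---|---|---|
| Root coverage | not listed in item 4 | none named | no |
| KT | calibrated examiners | practitioner | no |
| Thickness | calibrated examiners (TT1/TT2) | none named | no |
| PES | blinded, calibrated examiners | practitioner | yes |
| Patient-assessed esthetics | patient | patient | not applicable |
| Pain, swelling, activities and similar | patient | patient | not applicable |

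Count: 6 outcomes − 2 patient-reported = 4. Blinding is stated for 1 of 4 and is absent for 4 − 1 = 3.

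**2. Does the word practitioner settle who reads KT?** No. Section 4 uses it for PES too, and item 6 of the follow-up list assigns PES to blinded examiners. The word is compatible with a blinded examiner and with an unblinded one.

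**3. Does any other section supply the blinding?** No. The screening text requires training and calibration. The Visit 1 text names the surgeon. Neither addresses follow-up. Nothing says that the follow-up examiners did not operate or are kept unaware of allocation.

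**4. Pre-operative thickness.** The sequence in section 2 is consent, then envelope, then surgical visit, where the surgeon reads TT1/TT2. The plan does not say who opens the envelope, when the surgeon learns the arm, or how long after consent surgery takes place. Knowledge of the arm at this reading is therefore possible but not established. At most one of the six outcomes is affected.

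**5. Thickness method (a separate point).** Clinical parameters specifies sounding through the mucosa, and item 4 repeats TT1/TT2 at visits 5 to 7 with comparison to baseline. That series is consistent with itself. The section 4 outcome instead uses probing within the sulcus plus transparency, and no baseline by that method is described. It is unclear which series the change-in-thickness outcome uses.

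**6. Workload of the fix.** 40 patients × 2 visits (6 and 7) = 80 patient visits at most, before dropout. A blinded PES score is already required for each.

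**The case against.** The strongest reply is that the plan uses separate role words. The study surgeon acts at Visit 1, while examiners act at screening and follow-up. The surgeon is asked to confirm baseline KT, which suggests that someone else recorded it. On this reading the follow-up examiners are not the operator and may well be the people who score PES. This stands in part. A reader might infer from the KT wording that the operating surgeon measures the outcomes, and the documents do not support that inference. But separate role words do not state that different people fill the roles, and a non-operating examiner can still know the arm.

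A second reply is that root coverage could be read from the coded photographs taken at every visit, which would make blinding easy. That is possible, but the plan does not say so. Nor does it name an instrument for root coverage or KT, so these outcomes should not be described as probe readings.

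Third, blinding may be imperfect after visible surgery. At visits 6 and 7 the plan itself treats blinding as workable for PES. The section 4 outcomes for root coverage, KT and thickness are set at 6 and 12 months, so there is no need to extend the requirement to visits 4 and 5.

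Fourth, this is a pilot study. The sample-size text applies that label to the patient-centered outcomes; it also gives a formal non-inferiority calculation, so the label does not excuse the gap.

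**Conclusion.** The point holds as a gap in what the plan requires. Blinding is stated for one of the four outcomes that are not patient-reported and is missing for root coverage, KT and thickness. It should be corrected because the remedy is cheap and uses examiners the plan already calls for. It is not a fatal defect.

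Two stronger conclusions are tempting. One is that the readings are or will be biased; the documents only show that nothing guards against it. The other is a figure for the effect on error rates or power. The documents give no size for any assessor effect, and the sample-size statement does not name its endpoint, so such a figure would rest wholly on assumption and none is given here.

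The pre-operative thickness reading is a minor addition. The thickness-method conflict is real but is a matter of measurement definition, not blinding. The verdict assumes that no unseen examiner manual already assigns these readings to blinded staff. If one does, the protocol need only say so.

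**What to change.** 1. **Section 2, Follow up visits, item 4.** Keep the sentence "Clinical measurements will be collected by calibrated examiners" as it is, so that calibration remains unconditional at all visits. Add: *At visits 6 and 7, root coverage, KT and tissue thickness will be measured by blinded, calibrated examiners who did not operate on the patient; these may be the examiners who score PES.* This also brings root coverage into the follow-up list.
2. **Section 4.** In the KT bullet, replace the reference to a practitioner with *a blinded, calibrated examiner*. Name the same reader in the root coverage and thickness bullets.
3. **Section 2, Randomization (minor).** Add only that the allocation is not disclosed to the person recording pre-operative KT and TT1/TT2 until those values are recorded. Leave the rest of that paragraph, including the consent wording, unchanged.
4. **Thickness method (separate).** Reconcile Clinical parameters, follow-up item 4 and section 4 so that change in thickness uses one method, chosen by the investigators, at both baseline and follow-up.

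**Cost.** These are wording edits, with no change to sample size. If PES is scored chairside, the added work at visits 6 and 7 is small. If PES is scored from photographs, which the plan leaves open, an existing non-operating calibrated examiner must be scheduled for up to 80 patient visits. Under edit 3, if the surgeon remains the person recording thickness, the surgeon learns the arm only after the patient is anesthetized; having another calibrated person record it avoids this.

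### The keratinized tissue reading that admits a site appears also to be its baseline, so regression to the mean is expected to inflate the within-arm gain in both arms

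*Combined protocol and SAP*

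**What the plan says.** Section 2 (Procedures) has one combined visit: "Screening/baseline visit: patient's electronic records will be reviewed to assess radiographic documentation". At that visit, "Two trained and calibrated examiners will conduct clinical and radiographic evaluations to determine eligibility according to the above criteria". KT width is among the clinical parameters listed for capture. No rule is given for combining or repeating the examiners' readings.

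The inclusion criteria admit teeth with Miller class I or II "gingival recession defects and ≤ 2mm of KT at each site to be treated".

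The surgical visit text (Visit 1) adds a second look before grafting: "Study surgeon will confirm measurements taken at baseline with relation to width of keratinized tissue (KT"). This calls the earlier values the baseline. It does not say whether the second reading is recorded separately, taken without sight of the first, used to re-test eligibility, or used in the analysis.

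Follow up visits, item 4, schedules KT at visits 4 to 7 and states the comparison: "Measurements from all visits will be compared to baseline in order to evaluate the progression of healing over time up to 12 months post-op". Section 1 names the clinical outcomes as "percentage of root coverage, amount of KT increase, tissue thickness increase" and practitioner-assessed esthetics. Section 4 lists KT as a width in mm at 6 and 12 months, not as a change.

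**The concern.** When an upper cut-off is applied to an error-prone reading and that reading then serves as the baseline of a change score, the mean baseline lies below the mean true KT of the enrolled sites. A repeat reading would on average be higher with no treatment at all. Both arms are grafted, so no untreated group shows or removes this component.

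What is at stake is the KT gain reported for each technique. Taken at face value it would be somewhat too favourable, and so would any before-after test of it, although the plan names no such test.

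**Working it through.** **The plan's own figure.** Section 4 states 92% power with 20 per arm, margin -1.0, true difference 0.1, SD 1.0 and one-sided alpha 0.025. The noncentrality parameter is (1.0 + 0.1) / (1.0 × √(2/20)) = 3.479 on 38 degrees of freedom, which gives 92.4%. The figure reproduces, and nothing in it depends on how the KT baseline is defined.

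**Inputs for the artefact.** From the documents: the cut-off of 2 mm. Assumed, because the documents give no values: normal true KT at candidate sites with SD 1.0 mm and mean μ of 1.5 to 3 mm, and independent reading error with SD e of 0.3 to 0.7 mm.

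**Formula.** With s = √(1.0² + e²), ICC = 1.0²/s² and a = (2 − μ)/s:

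spurious gain = (1 − ICC) × s × φ(a)/Φ(a)

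**Middle case, μ = 2.5 and e = 0.5.**
- s = √1.25 = 1.118; ICC = 1/1.25 = 0.80; a = −0.5/1.118 = −0.447.
- φ(a)/Φ(a) = 0.361/0.327 = 1.103.
- Mean admitting reading: 2.5 − 1.118 × 1.103 = 1.267 mm.
- Mean true KT of the admitted sites: 2.5 − 0.80 × 1.118 × 1.103 = 1.514 mm.
- Spurious gain: 0.20 × 1.118 × 1.103 = 0.247 mm.

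A simulation of this case with whole-millimetre readings floored at zero gave a first reading of 1.556 mm, a second of 1.795 mm, and a difference of 0.24 mm.

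**Grid (mm per arm).**

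| Candidate mean | e = 0.3 | e = 0.5 | e = 0.7 |
|---|---|---|---|
| 1.5 | 0.045 | 0.120 | 0.223 |
| 2.0 | 0.069 | 0.178 | 0.320 |
| 2.5 | 0.097 | 0.247 | 0.432 |
| 3.0 | 0.129 | 0.322 | 0.555 |

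**Sensitivity to reliability.** Fixing the total SD (true plus error) at 1.0 mm and letting the ICC run from 0.95 to 0.70 over the same means gives 0.025 to 0.458 mm. At ICC 0.95 it is never above 0.076 mm.

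**Which reading is the baseline (middle case).**

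| Rule | Spurious gain |
|---|---|
| Screening reading | 0.25 mm |
| Mean of screening and visit 1 readings | 0.12 mm |
| Both readings must be at most 2 mm, either one used as baseline | 0.15 mm |
| Independent visit 1 reading, not used for selection | 0.00 mm |

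**Between arms.** Selection comes before the effect of allocation and is the same in both arms, so the expected shift in the difference is zero. In 20,000 simulated trials of 20 against 20 (total SD 1.0, mean 2.5, ICC 0.80) the mean between-arm difference in gain was 0.003 mm, with a Monte Carlo standard error of 0.001.

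**The case against.** The strongest reply is that this touches no inference the plan specifies. The purpose is to compare two randomized techniques, the only stated test is a two-sample non-inferiority t-test, the section 4 KT outcome is an absolute width, and the comparison with baseline is worded as a description of healing. All of that stands. It confines the point to the within-arm gain, but does not remove it: section 1 names the KT increase as an outcome, and item 4 plans the comparison with baseline.

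Second, visit 1 already includes a KT confirmation before grafting. If that reading were independent, unused for selection and taken as baseline, there would be no artefact. The plan does not say so, and it calls the earlier values the baseline. This is why inflation is the expected result on the natural reading rather than a certainty.

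Third, the size rests wholly on assumptions. Patients are first identified at a routine appointment against the inclusion criteria, so the screened pool may already be low in KT; at a candidate mean of 1.5 mm the range is 0.045 to 0.223 mm. If the two examiners' readings were averaged, which the plan does not state, the middle case falls from 0.25 to 0.13 mm. This also stands, and the top of the grid needs both a 3 mm candidate mean and an error SD of 0.7 mm.

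A reader might go further and infer that the non-inferiority conclusion is biased, or might measure the artefact against the 1.0 margin. The documents support neither. The artefact is expected to be equal in both arms and cancels in the contrast. The margin is a between-arm quantity for which section 4 names no endpoint or unit.

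**Conclusion.** The point holds for the within-arm KT gain only. On the natural reading of the plan, that gain is expected to be biased upward by the same amount in each arm. The size is 0.045 to 0.555 mm under the stated assumptions, and below 0.1 mm if readings are highly reliable. The direction follows from the design as long as readings carry any error; the size cannot be settled from the documents, which report no repeatability. The between-arm comparison, the absolute KT width outcome and the power statement are not biased by it. It is worth correcting because a stated comparison is affected and the remedy is almost free.

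**What to change.** - Use the screening KT reading for eligibility only.
- Record the visit 1 KT reading, before grafting, as a separate value. Take it without sight of the screening value, do not use it to exclude sites, and name it as the baseline for KT change at visits 4 to 7.
- Preferably have a calibrated examiner take it, as at follow-up, and before the local infiltration, so that baseline and follow-up readings are made under like conditions. Because the envelope is opened after consent, this reading may follow allocation; the examiner should not know the arm.
- State that within-arm KT gain is descriptive and that conclusions about the techniques rest on the between-arm comparison.

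The cost is one recorded reading at an existing visit, a few sentences in the protocol, and a slightly smaller reported gain.
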